Appendix

Baseline Examination Data

Pt. ID # _____

Treatment Group

Vaginal Laser Vaginal Estrogen

Age _____ BMI _____

Race

Caucasian African-American Hispanic Asian

Other, specify _____

Marital status

Single Married Divorced Widowed

Menopausal Status

Premenopausal Perimenopausal Postmenopausal (no menses for 6 months)

Current use of oral or transdermal hormonal therapy

Yes No

History of vaginal estrogen use

Yes No

Sexually active

Yes No

Exam:

Vaginal pH _____

Vaginal caliber XS S M L XL

Maturation Index Results:

_____ Data prior to and after Vaginal Laser or Vaginal Estrogen therapy (6 wk, 3 mos, 6 mos):

Exam

Vaginal pH _____

Vaginal caliber XS S M L XL

Local anesthetic used? Yes No N/A (Estrogen arm)

Vulvovestibular laser therapy? Yes No N/A (Estrogen arm)

Adverse event laser arm:

Inability to complete the procedure due to discomfort or constricted vagina

Yes No

Other: Specify _____

PATIENT ID: _____

PATIENT GLOBAL IMPRESSION OF IMPROVEMENT

Patient Global Impression of Improvement

Circle how you feel your symptoms are after treatment:

Much Worse	Worse	Same	Better	Much Better
1	2	3	4	5

Level of satisfaction after treatment

How would you define the level of satisfaction with the treatment?

Very Dissatisfied	Dissatisfied	Same	Satisfied	Very Satisfied
1	2	3	4	5

10 cm VISUAL ANALOG SCALE (VAS)

0 indicating absent symptoms (no bother) and 10 indicating the worst the symptoms could be (bothers as much as you can imagine). Please indicate your degree of bother with an X marked on the 10 cm line below next to each symptom.

	No Bother	Mild Bother	Moderate Bother	Most Bother
Vaginal dryness	0			10
Vaginal itching	0			10
Vaginal irritation	0			10
Painful urination	0			10

Additional question regarding sexual function not included in the FSFI.
This question will be asked at baseline, 6 weeks, 3 months, and 6 months.

Over the past 4 weeks have you been sexually active? (yes/no)

The reason if your answer no

- no partner
- no interest
- due to pain
- due to other reason, please specify_____

VAGINAL HEALTH INDEX SCALE

	Overall elasticity*	Fluid secretion type & consistency	pH	Epithelial mucosa	Moisture
1	None	None	6.1	Petechiae noted before contact	None, mucosa inflamed
2	Poor	Scant, thin yellow	5.6 – 6.0	Bleeds with light contact	None, mucosa not inflamed
3	Fair	Superficial, thin white	5.1 – 5.5	Bleeds with scraping	Minimal
4	Good	Moderate, thin white	4.7 – 5.0	Not friable, thin mucosa	Moderate
5	Excellent	Normal (white flocculent)	≤ 4.6	Not friable, normal mucosa	Normal

*Lower score corresponds to greater urogenital atrophy
Bachmann G. Maturitas 1995; 22:Suppl S1-5.

Female Sexual Function Index (FSFI) ©

Subject Identifier _____

Date _____

INSTRUCTIONS: These questions ask about your sexual feelings and responses during the past 4 weeks. Please answer the following questions as honestly and clearly as possible. Your responses will be kept completely confidential. In answering these questions the following definitions apply:

Sexual activity can include caressing, foreplay, masturbation and vaginal intercourse.

Sexual intercourse is defined as penile penetration (entry) of the vagina.

Sexual stimulation includes situations like foreplay with a partner, self-stimulation (masturbation), or sexual fantasy.

CHECK ONLY ONE BOX PER QUESTION.

Sexual desire or interest is a feeling that includes wanting to have a sexual experience, feeling receptive to a partner's sexual initiation, and thinking or fantasizing about having sex.

1. Over the past 4 weeks, how **often** did you feel sexual desire or interest?

- Almost always or always
- Most times (more than half the time)
- Sometimes (about half the time)
- A few times (less than half the time)
- Almost never or never

2. Over the past 4 weeks, how would you rate your **level** (degree) of sexual desire or interest?

- Very high
- High
- Moderate
- Low
- Very low or none at all

Sexual arousal is a feeling that includes both physical and mental aspects of sexual excitement. It may include feelings of warmth or tingling in the genitals, lubrication (wetness), or muscle contractions.

3. Over the past 4 weeks, how **often** did you feel sexually aroused ("turned on") during sexual activity or intercourse?

- No sexual activity
- Almost always or always
- Most times (more than half the time)
- Sometimes (about half the time)
- A few times (less than half the time)
- Almost never or never

4. Over the past 4 weeks, how would you rate your **level** of sexual arousal ("turn on") during sexual activity or intercourse?

- No sexual activity
- Very high
- High
- Moderate
- Low
- Very low or none at all

5. Over the past 4 weeks, how **confident** were you about becoming sexually aroused during sexual activity or intercourse?

- No sexual activity
- Very high confidence
- High confidence
- Moderate confidence
- Low confidence
- Very low or no confidence

6. Over the past 4 weeks, how **often** have you been satisfied with your arousal (excitement) during sexual activity or intercourse?

- No sexual activity
- Almost always or always
- Most times (more than half the time)
- Sometimes (about half the time)
- A few times (less than half the time)
- Almost never or never

7. Over the past 4 weeks, how **often** did you become lubricated ("wet") during sexual activity or intercourse?

- No sexual activity
- Almost always or always
- Most times (more than half the time)
- Sometimes (about half the time)
- A few times (less than half the time)
- Almost never or never

8. Over the past 4 weeks, how **difficult** was it to become lubricated ("wet") during sexual activity or intercourse?

- No sexual activity
- Extremely difficult or impossible
- Very difficult
- Difficult
- Slightly difficult
- Not difficult

9. Over the past 4 weeks, how often did you **maintain** your lubrication ("wetness") until completion of sexual activity or intercourse?

- No sexual activity
- Almost always or always
- Most times (more than half the time)
- Sometimes (about half the time)
- A few times (less than half the time)
- Almost never or never

10. Over the past 4 weeks, how **difficult** was it to maintain your lubrication ("wetness") until completion of sexual activity or intercourse?

- No sexual activity
- Extremely difficult or impossible
- Very difficult
- Difficult
- Slightly difficult
- Not difficult

11. Over the past 4 weeks, when you had sexual stimulation or intercourse, how **often** did you reach orgasm (climax)?

- No sexual activity
- Almost always or always
- Most times (more than half the time)
- Sometimes (about half the time)
- A few times (less than half the time)
- Almost never or never

12. Over the past 4 weeks, when you had sexual stimulation or intercourse, how **difficult** was it for you to reach orgasm (climax)?

- No sexual activity
- Extremely difficult or impossible
- Very difficult
- Difficult
- Slightly difficult
- Not difficult

13. Over the past 4 weeks, how **satisfied** were you with your ability to reach orgasm (climax) during sexual activity or intercourse?

- No sexual activity
- Very satisfied
- Moderately satisfied
- About equally satisfied and dissatisfied
- Moderately dissatisfied
- Very dissatisfied

14. Over the past 4 weeks, how **satisfied** have you been with the amount of emotional closeness during sexual activity between you and your partner?

- No sexual activity
- Very satisfied
- Moderately satisfied
- About equally satisfied and dissatisfied
- Moderately dissatisfied
- Very dissatisfied

15. Over the past 4 weeks, how **satisfied** have you been with your sexual relationship with your partner?

- Very satisfied
- Moderately satisfied
- About equally satisfied and dissatisfied
- Moderately dissatisfied
- Very dissatisfied

16. Over the past 4 weeks, how **satisfied** have you been with your overall sexual life?

- Very satisfied
- Moderately satisfied
- About equally satisfied and dissatisfied
- Moderately dissatisfied
- Very dissatisfied

17. Over the past 4 weeks, how **often** did you experience discomfort or pain during vaginal penetration?

- Did not attempt intercourse
- Almost always or always
- Most times (more than half the time)
- Sometimes (about half the time)
- A few times (less than half the time)
- Almost never or never

18. Over the past 4 weeks, how **often** did you experience discomfort or pain following vaginal penetration?

- Did not attempt intercourse
- Almost always or always
- Most times (more than half the time)
- Sometimes (about half the time)
- A few times (less than half the time)
- Almost never or never

19. Over the past 4 weeks, how would you rate your **level** (degree) of discomfort or pain during or following vaginal penetration?

- Did not attempt intercourse
- Very high
- High
- Moderate
- Low
- Very low or none at all

Thank you for completing this questionnaire

Medicine Compliance Log:

Weeks 1 and 2, please place an X in the box for each day you inserted vaginal cream or tablet

Weeks 3-6

Weeks 7-12

Weeks 13-18

Weeks 19-24

Urogenital Distress Inventory (UDI-6 Short Form): UDI-6

- 1) Do you usually experience frequent urination? Yes No
If yes, how much does this bother you? Not at all Somewhat
Moderately Quite a bit
- 2) Do you usually experience urine leakage associated with a feeling of urgency; that is, a strong sensation of needing to go to the bathroom? Yes No
If yes, how much does this bother you? Not at all Somewhat
Moderately Quite a bit
- 3) Do you usually experience urine leakage related to coughing, sneezing, or laughing?
Yes No
If yes, how much does this bother you? Not at all Somewhat
Moderately Quite a bit
- 4) Do you experience small amounts of urine leakage (that is, drops)? Yes No
If yes, how much does this bother you? Not at all Somewhat
Moderately Quite a bit
- 5) Do you experience difficulty emptying your bladder? Yes No
If yes, how much does this bother you? Not at all Somewhat
Moderately Quite a bit
- 6) Do you usually experience pain or discomfort in the lower abdomen or genital region?
Yes No
If yes, how much does this bother you? Not at all Somewhat
Moderately Quite a bit
If yes, then is your pain relieved after emptying your bladder? Yes No

No= 0, Not at all= 1, Somewhat= 2, Moderately= 3, Quite a bit= 4

Add all scores and multiply by 6 then multiply by 25 for the scale score

Missing items are dealt with by using the mean from the answered items only

Higher score = higher disability

Also see scoring of PFDI-20.

Grade A rating for symptoms of UI for women

Donavan J, et al Symptom and quality of life assessment. In *Incontinence vol 1 Basics and Evaluation* eds Abrams P, Cardozo L, Khoury S, Wein A. Health Publications Ltd Paris France 2005.

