In addition to a standardized evaluation including the history and physical examination, patients will be asked to complete the Female Sexual Function Inventory (FSFI) questionnaire, the Day-to-day Impact of Vaginal Aging (DIVA) questionnaire, and the Urogenital Distress Inventory (UDI-6), at baseline, 3 months, and 6 months after baseline and visual analog scales (VAS) for GSM symptoms. The Patient Global Index (PGI) will also be administered at 6 months. Completion of these questionnaires should take no more than 15-20 minutes. A vaginal maturation index will be obtained at the baseline visit on a regular Pap Smear slide and fixed with cytofixative and air dried. This will be repeated during the last follow up visit at 6 months.

Vaginal Laser Protocol

Postmenopausal women will undergo treatment intravaginally with the fractional microablative CO₂ laser system (SmartXide 2 V 2 LR, MonaLisa Touch, DEKA, Florence, Italy), using the following setting: dot power 30 watt, dwell time 1000 μ s, dot spacing 1000 μ m and the smart stack parameter from 1 to 3. Stack 1 is used at baseline and stack 3 at 6 weeks and 3 months. The laser beam will be applied using a 90° vaginal probe gently inserted up to the top of the vaginal canal and subsequently withdrawn at centimeter intervals and rotated to 6 positions in an alternating clockwise and counterclockwise pattern in order to provide a complete treatment of the vaginal wall. At the investigators discretion a flat probe (vulvar probe) may be utilized to more efficiently treat the introital area and vestibule. At the level of the vaginal introitus, the dot power will be decreased to 26 watts. A treatment cycle includes three laser applications (every 40-50 days, approximately 6 weeks). The procedure will be performed in the outpatient clinic and does not require any specific preparation (e.g. analgesia/anesthesia). At the clinician's discretion, EMLA cream may be applied to introitus for thirty minutes and wiped clean and dried prior to vulvar laser therapy. Patients will be recommended to avoid coital sexual activity for at least 3 days after each laser application because a mild inflammatory reaction may last up to 48 hours after laser therapy. Topical lidocaine 5% ointment may be used for any vulvar pain post-procedure.

Post Treatment Instructions

- Each subject shall be evaluated immediately post-treatment for complications and side effects, excessive bleeding, symptomatic vaginal discharge, pain, etc.

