⁴Estradiol vaginal tablet (Vagifem[®]): one tablet (10 microgram) inserted daily into the vagina for two weeks (fourteen days) then 1 tablet inserted intravaginally twice weekly for 24 + 2 additional weeks.

Data Collection & Management:

Baseline data will include the following:

- Patient age, race, vaginal parity, menopausal state, BMI, history of previous use of vaginal estrogen
- FSFI, DIVA, and UDI-6 questionnaires
- VAS for GSM symptoms and VHI for objective GSM findings

Data points recorded during the procedure will include:

- Likert Scales for physician assessment of patient comfort during the procedure.
- Adverse events including inability to complete the procedure due to discomfort or constricted vagina

Post-procedure data will include the following:

- The rate of satisfaction of patients with treatment by mean of the Patient Global Impression of Improvement (PGI), using a 5-point Likert scale.
- The degree of difficulty encountered by the physician in performing the treatment, by mean of a 5-point Likert scale.
- Additionally, untoward side effects of treatment such as new bothersome vaginal irritation and significant vaginal bleeding will be recorded.

Protection of each subject's personal health information will be a priority in this study. One master Excel file containing subject personal information including name and medical record number will be kept in a password-protected file, on a designated protected research drive on a password-protected computer in a locked office at each respective institution. In that file, each subject will be assigned a subject identification number that will be used for the purposes of data collection in order to de-identify subjects.

All paper forms used for data collection will be kept in a research cabinet dedicated to this project, which will be locked at all times, in a locked office at the Cleveland Clinic (or other institution). All forms will contain de-identified information. Identification numbers will correspond to the subjects listed in the master excel file.

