This study is a non-inferiority study design. The predefined non-inferiority margin is a difference of 1.0cm on a 10cm VAS. To minimize bias towards a finding of non-inferiority, data from women who were eligible and received the assigned treatment (per protocol) will be used for the analysis of the primary outcome. The primary outcome will be presented as the difference in VAS scores between treatments (Vaginal Estrogen – Vaginal Laser). The hypothesis of non-inferiority of the two treatment groups will be tested by comparing the lower limit of the two-sided 95% confidence interval (equivalent of a one-sided significance level of 0.025%) of the absolute difference with the margin set at -1.0cm. A secondary analysis of the primary outcome according to original treatment assignment (intent to treat) will also be performed as well as standard superiority testing using Student's t-test. If differences in baseline patient characteristics are noted, linear regression analysis adjusting for these differences will also be performed. Secondary outcomes will be analyzed using the intent to treat population using Pearson's Chi-square test for categorical data, Student's t-test for parametric continuous data, or Wilcoxon rank sum test for ordinal or nonparametric continuous data. Changes in patient reported outcome questionnaires (FSFI, DIVA, UDI-6, etc.) will be compared between treatments using repeated measures ANCOVA.

SAFETY AND ADVERSE EVENTS

Definitions

Adverse events include prolonged vaginal bleeding beyond 48 hours, heavy vaginal bleeding, bothersome vaginal irritation, bacterial vaginosis, vaginal yeast infection, post-procedural fever, and skin burn.

Recording of Adverse Events

At each contact with the subject, the investigator will seek information on adverse events by specific questioning and, as appropriate, by examination. Information on all adverse events will be recorded immediately in the source document, and also in the appropriate adverse event section of the case report form (CRF). All clearly related signs, symptoms, and abnormal diagnostic procedures results will also be recorded in the source document.

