The clinical course of each event will be followed until resolution, stabilization, or until it has been determined that the study treatment or participation is not the cause. Serious adverse events that are still ongoing at the end of the study period will be followed up to determine the final outcome. Any serious adverse event that occurs up to 30 days after the subjects final study visit, and is considered to be related to or possibly related to the study treatment or study participation, will be recorded and reported immediately.

Reporting of Serious Adverse Events

Notification to Data Coordinating Center

A Serious Adverse Event (SAE) form must be completed by the investigator and emailed to the DCC within 24 hours. The investigator will keep a copy of this SAE form on file at the study site. Report serious adverse events by email to:

[name] – [contact]

[name] – [contact]

At the time of the initial report, the following information should be provided:

- Study identifier
- Study Center
- Subject number
- A description of the event
- Date of onset
- Current status
- Whether study treatment was discontinued
- The reason why the event is classified as serious
- Investigator assessment of the association between the event and study treatment

Within the following 48 hours, the investigator must provide further information on the serious adverse event in the form of a written narrative. This should include a copy of the completed Serious Adverse Event form, and any other diagnostic information that will assist the understanding of the event. Significant new information on ongoing serious adverse events should be provided promptly to the DCC.

DATA SAFETY MONITORING

The Data Safety Monitoring Board (DSMB) is the primary data and safety advisory group for the **Female Foundation for Health Awareness (FFHA)** trial entitled "**A Randomized Clinical Trial Comparing Vaginal Laser Therapy to Vaginal Estrogen Therapy (VeLVET) in Women with Genitourinary Syndrome of Menopause (GSM)**". The DSMB reviews study data, evaluates the treatments for excess adverse experiences according to treatment group, judges whether the overall integrity and conduct of the study remain acceptable and makes recommendations to the FFHA and the Cleveland Clinic Data Coordinating Center.

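### The shared follow-up form heads its only adverse-event section for the laser arm, against the protocol's arm-neutral rules for collecting adverse events

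*Combined protocol and SAP*

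**What the plan says.** The follow-up sheet in the Appendix is headed "Data prior to and after Vaginal Laser or Vaginal Estrogen therapy (6 wk, 3 mos, 6 mos"), so it serves both arms. Two of its items, on local anesthetic and vulvovestibular laser, offer a not-applicable choice for the estrogen arm. The adverse-event block comes next under the heading "Adverse event laser arm". It has one pre-printed yes/no item, "Inability to complete the procedure due to discomfort or constricted vagina", and then a free-text line for anything else.

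The protocol body draws no such line between arms:

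- *Calendar of Study Procedures*: adverse events are marked at baseline, 6 weeks, 3 months and 6 months with no arm restriction. The two Likert rows in the same table are labelled as laser rows.
- *Recording of Adverse Events*: at each contact the investigator asks specifically about adverse events. All of them go into the source document and "in the appropriate adverse event section of the case report form (CRF").
- *Definitions*: seven events are named, namely bleeding beyond 48 hours, heavy bleeding, bothersome irritation, bacterial vaginosis, yeast infection, post-procedural fever and skin burn.
- *Data Safety Monitoring*: the board "evaluates the treatments for excess adverse experiences according to treatment group".

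**The concern.** The form distinguishes the arms elsewhere, so the laser-only heading reads as deliberate. A coordinator who follows the print could leave the block blank for an estrogen-arm woman, and a blank does not show whether she was asked and had no event or was never asked.

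What is at stake is the safety comparison. Yeast infection, bacterial vaginosis, irritation and bleeding can occur under either treatment. If they are written down more completely in one arm, the difference in reported rates reflects the form as well as the treatments. Under-recording in the estrogen arm would hide estrogen harms and make laser look worse. Events that were never asked about cannot be reliably recovered later.

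**Working it through.** The plan states no figure on this point, so the main check is to set the texts side by side.

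1. **Who the form is for.** Its title names both therapies and three visits. It is not a laser procedure record.
2. **Who the adverse-event block is for.** Its heading names the laser arm. No estrogen or arm-neutral adverse-event heading is printed on the sheet.
3. **What the block asks.** None of the seven defined events is printed. The one pre-printed item concerns completing the procedure. The calendar schedules no laser session at 6 months, so at that visit the item fits neither arm. The specific questioning promised in the text has no questions on this sheet.
4. **Whether another printed sheet fills the gap.** The estrogen-arm compliance log tracks insertions only. The visual analog scale has an irritation line for all women, but it is a symptom score. Under *Data Collection & Management*, "Adverse events including inability to complete the procedure due to discomfort or constricted vagina" is listed among data recorded during the procedure. The separate SAE form covers serious events only.
5. **Whether contact is otherwise equal.** "Each subject shall be evaluated immediately post-treatment for complications and side effects" stands under *Post Treatment Instructions* in the laser protocol, which has three sessions. No estrogen counterpart is described. These checks fall at visits where adverse events are scheduled for both arms, so they add a look but no visit.

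Steps 1 to 3 conflict with the calendar and with the rule on recording all events. Step 4 finds no other printed form that resolves the conflict for non-serious events.

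**Illustration of what unequal recording could do.** Inputs: 196 women are to be randomized, so 196 / 2 = 98 per arm at 1:1. The true risk p is the same in both arms (assumed). The share of estrogen-arm events recorded is c (assumed). Laser capture is complete (assumed).

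Reported rates are p for laser and p × c for estrogen, so the false excess is p − p × c = p(1 − c). The chance that a two-sided 5% test points against laser is approximately

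Φ{ [p(1 − c) − 1.96 × √(2m(1 − m)/98)] / √([p(1 − p) + pc(1 − pc)]/98) }, where m = (p + pc)/2.

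For p = 0.20 and c = 0.75, the rates are 0.20 and 0.15 and m = 0.175. The chance is Φ{(0.05 − 1.96 × 0.0543)/0.0542} = Φ(−1.04), about 15%.

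| True risk, both arms | Estrogen capture | Reported laser vs estrogen | False excess | Chance of significance against laser |
|---|---|---|---|---|
| 20% | 100% | 20% vs 20% | 0 points | 2.5% |
| 20% | 75% | 20% vs 15% | 5 points | about 15% |
| 20% | 50% | 20% vs 10% | 10 points | about 50% |
| 10% | 75% | 10% vs 7.5% | 2.5 points | about 9% |
| 10% | 50% | 10% vs 5% | 5 points | about 26% |

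Only a gap in capture between the arms matters here. Equal capture, even if incomplete, gives no false difference when the true risks are equal.

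**The case against.** A reader might infer that estrogen-arm events have no field anywhere, and that the safety comparison is biased by design. The documents support neither.

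- **No field anywhere.** The CRFs are held in REDCap and their fields are not shown. The appendix is not the full form set: it lacks the SAE form and the Likert forms for discomfort and ease of treatment. The protocol promises only that the questionnaires are in the appendix. Absence from one sheet is therefore not absence from the plan.
- **Biased by design.** The written design prescribes the same questioning, schedule and recording in both arms. Bias would come from following the sheet instead of the text, so it is a risk and not a demonstrated result.
- **The asymmetry on the sheet is narrow.** It pre-prints none of the seven defined events for either arm. The free-text line has no arm label of its own, and the original layout cannot be judged from extracted text. In practice the issue may come down to who uses that line.
- **Some coverage exists.** Irritation is scored for all women on the visual analog scale, and serious events have an arm-neutral form. The *Analysis Plan* specifies no by-arm test of adverse events, and the primary outcome is unaffected.

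All of this stands, and it limits the point to an inconsistency with a foreseeable risk. It does not remove the inconsistency. Paper forms are part of the data flow, and nothing shown establishes that the REDCap page is arm-neutral. The board is charged with comparing groups whether or not a formal test is planned.

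**Conclusion.** The point holds as an internal contradiction. The appendix follow-up form serves both arms but heads its only adverse-event section for laser, while the calendar and the recording rule apply to every woman. Completed as printed, the form puts non-serious estrogen-arm events at risk of under-recording relative to laser, and the by-group safety review would inherit that distortion.

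The size cannot be determined from the documents. The tabulated figures rest on assumed risks, assumed capture and complete laser recording. They show only that a moderate gap could produce an apparent laser excess of several points, and that there is no such bias if capture is equal. The change is worth making before data collection because it is cheap and the loss would be hard to repair.

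**What to change.** - Retitle the section *Adverse events (both arms)*. List the seven defined events plus an other category as yes/no items, asked identically of every woman at 6 weeks, 3 months and 6 months. Fever and burn are defined partly in procedural terms, so word them neutrally enough to be asked in both arms.
- Keep inability to complete the procedure as a separate laser-only item with a not-applicable box for the estrogen arm, as the neighboring laser items already have.
- Report findings from the immediate post-session checks separately, and base the by-arm comparison on the items asked the same way in both arms.
- Confirm that the REDCap adverse-event form is the same in both arms and matches the revised sheet.

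The cost is one form revision and a few more questions per visit. It needs no new visits and changes nothing about treatment.

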This is a multi-centered, randomized prospective single blinded clinical trial comparing CO2 fractionated vaginal laser therapy and vaginal estrogen therapy in the treatment of vulvovaginal atrophy/GSM

Study Outcomes:

The primary outcome is subjective improvement of vaginal dryness using a 10 cm Visual analog scale.

The secondary outcomes that will be assessed include

1. An objective evaluation of vaginal atrophy/estrogenization measured by the globally validated “Vaginal Health Index” (VHI) score [reference Bachmann Maturitas 1995 attached]
2. The effect of GSM symptoms on QoL using the DIVA questionnaire [28]
3. The effect of treatment on the vaginal maturation index, at baseline and 6 month follow up
4. The effect of treatment on vaginal wall elasticity, using standard vaginal dilators to determine vaginal caliber
5. The effect of treatment on the female sexual function, by means of the Female Sexual Function Index (FSFI)[29]
6. Calculation of the percentage of patients who are sexually active or resume intercourse after therapy. A sexual function question not included in FSFI has been added to evaluate this.
7. The effect of the treatment on urinary symptoms by means of the Urogenital Distress Inventory (UDI-6) [30]
8. The degree of difficulty encountered by the physician in performing the MonaLisa laser treatment assessed via a 5-point Likert scale,
9. The rate of satisfaction of patients with treatment assessed by the Patient Global Impression of Improvement (PGI), using a 5-point Likert scale.

Subject SelectionInclusion Criteria

- Menopausal with absence of menstruation for at least 12 months
- Presence of vaginal atrophy symptoms [subjective assessment of vaginal dryness ≥ 7 cm on VAS)
- Prolapse stage \leq II, according to the pelvic organ prolapse quantification (POP-Q) system[31]
- No pelvic surgery within 6 months prior to treatment (vulva biopsy may be included after 2 weeks)
- Understanding and acceptance of the obligation to return for all scheduled follow-up visits

- English speaking and able to give informed consent

Exclusion Criteria

- Personal history of vulvovaginal condyloma, vaginal intraepithelial neoplasia (VAIN), vaginal carcinoma, lichen sclerosis, lichen planus, history of vaginal radiation, history of cervical cancer, other gynecologic cancer, or pelvic radiation
- Acute or recurrent urinary tract infection (UTI), or genital infection (e.g. bacterial; vaginosis, herpes genitalis, candida).

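### The question assigned to secondary outcome 6 gives a valid percentage sexually active but cannot support a statement about resumed intercourse, and the planned test leaves the baseline answer unused

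*Combined protocol and SAP*

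**What the plan says.** Study Outcomes, secondary outcome 6, reads: "Calculation of the percentage of patients who are sexually active or resume intercourse after therapy". The next sentence names the instrument: "A sexual function question not included in FSFI has been added to evaluate this".

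The Appendix prints that item under the label "Additional question regarding sexual function not included in the FSFI", with the schedule "This question will be asked at baseline, 6 weeks, 3 months, and 6 months". The item is: "Over the past 4 weeks have you been sexually active? (yes/no". A woman who answers no is asked for a reason; the options include having no partner and pain. No definition of the term is printed with the item.

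The FSFI instructions, also in the Appendix, keep two terms apart: "Sexual activity can include caressing, foreplay, masturbation and vaginal intercourse", and "Sexual intercourse is defined as penile penetration (entry) of the vagina". FSFI items 17 to 19 offer the response "Did not attempt intercourse". The Calendar of Study Procedures places the FSFI at baseline, 3 months and 6 months, and sexual activity at all four visits.

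For categorical secondary outcomes the Analysis Plan specifies Pearson's chi-square in the intent-to-treat population. It gives no rule for deriving outcome 6: no denominator, no time point, no use of the baseline answer and no link to the FSFI items.

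**The concern.** The outcome names two things and its instrument measures one. A yes to the added question may or may not involve intercourse, so the item cannot show that intercourse was resumed. If the result were reported under that label, women active without intercourse would be counted as successes.

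Resuming also implies a change from an earlier state. The baseline answer is collected, but the planned test compares arms without it. Women who were active from the start contribute to the percentage in both arms and say nothing about resumption. A real difference among women inactive at baseline would look smaller, and the comparison would be less able to detect it. With no rule fixed in advance, the definition could also be settled after the data are seen.

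**Working it through.** The documents state no expected rate, sample size or power for outcome 6, so there is no plan figure to reproduce. The check has three steps.

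**1. What the question can return.** By the FSFI definitions, intercourse is one form of sexual activity. The set of women who are active or have intercourse is therefore the set who are active. Read as a union, the outcome is measured by the added question without error, and the words about intercourse add nothing to it.

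**2. What happens if the result is labelled as intercourse.** Let A be the share answering yes and q the share of those women without intercourse. The overstatement is A × q. Neither value is in the documents. Assumed ranges are A = 40% to 80% and q = 0% to 30%:

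| A | q = 0% | q = 10% | q = 20% | q = 30% |
|---|---|---|---|---|
| 40% | 0 | 4 | 8 | 12 |
| 60% | 0 | 6 | 12 | 18 |
| 80% | 0 | 8 | 16 | 24 |

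Entries are percentage points. For example, A = 60% and q = 20% gives 60% reported against 60% × 0.80 = 48% with intercourse, a gap of 12 points.

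**3. What leaving out the baseline answer does.** Let b be the share active at baseline, taken as equal in the two arms. Then:

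difference over all women = b × (difference among those active at baseline) + (1 − b) × (difference among those inactive at baseline).

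Assume that women active at baseline stay active in both arms, so the first term is zero, and that the true difference among the others is 25 points:

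| b | (1 − b) × 25 points |
|---|---|
| 40% | 15 |
| 50% | 12.5 |
| 60% | 10 |
| 70% | 7.5 |

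To see the effect on power, take b = 60% and resumption of 50% against 25% among the inactive. The all-women percentages are 0.60 + 0.40 × 0.50 = 80% and 0.60 + 0.40 × 0.25 = 70%. The Sample Size Rationale has 85 women per group, of whom 0.40 × 85 = 34 would be inactive at baseline. By normal approximation at two-sided 5%:

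- All women, 80% against 70%, 85 per arm. Null standard error √(2 × 0.75 × 0.25 / 85) = 0.0664; alternative standard error √((0.16 + 0.21) / 85) = 0.0660. (1.96 × 0.0664 − 0.10) / 0.0660 = 0.46, so power is about 32%.
- Inactive at baseline, 50% against 25%, 34 per arm. Null standard error √(2 × 0.375 × 0.625 / 34) = 0.1174; alternative standard error √((0.25 + 0.1875) / 34) = 0.1134. (1.96 × 0.1174 − 0.25) / 0.1134 = −0.18, so power is about 57%.

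In this scenario the smaller group is the more informative one for resumption.

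**The case against.** A reader might infer that the reported percentage will be wrong. The documents do not support that. The two parts of the outcome are joined by *or*, the union equals sexual activity, and the question measures it directly. An error arises only if the result is presented as intercourse, and no section says it will be.

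A reader might also say that the trial itself defines sexual activity broadly for this item. It does not. The broad definition is given for answering the FSFI, and the added question is labelled as outside the FSFI. For the added item the term is simply undefined.

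Nor does the plan rule out estimating resumption. The item is asked at baseline and at every follow-up, so a no-to-yes change in activity can be derived. The plan is silent on whether it will be.

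The difference over all women is not an error either. It is a correct answer to a different question, and the dilution figures rest on assumed rates. The outcome is one of nine secondary outcomes, with no stated hypothesis or power.

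All of this stands. It leaves two points untouched: the assigned item cannot identify intercourse, and the only test named for a categorical outcome does not use the baseline answer. The repeated measures ANCOVA in the Analysis Plan does not fill the gap, because it is specified for changes in the questionnaires, and a yes/no answer falls under the categorical rule.

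**Conclusion.** The point holds in a limited form. The percentage sexually active will be valid, but it cannot support a statement about resumed intercourse, and the unadjusted chi-square dilutes any difference in resumption.

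The dilution factor is one minus the share active at baseline. A 25-point difference among inactive women becomes 15 down to 7.5 points over all women when 40% to 70% are active at baseline, provided that those women stay active. Mislabelling activity as intercourse would overstate it by 0 to 24 points over the assumed ranges. Neither size can be computed from the documents alone. The primary analysis is unaffected. This is a worthwhile refinement and not a threat to the trial's conclusion.

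**What to change.** Replace the single percentage in the SAP with separately labelled results:

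- **(a) Sexual activity.** Report the percentage sexually active at 6 months from the added question, compared between arms with adjustment for the baseline answer, for example by logistic regression. Report alongside it the no-to-yes change among women inactive at baseline. State what the term means for this item. The baseline examination form also records sexual activity, so say which baseline record is used.
- **(b) Attempted intercourse.** Among women whose baseline answer to FSFI items 17 to 19 was "Did not attempt intercourse", report the percentage giving any other answer at 6 months. Label it as attempted intercourse, and state in advance how mixed answers across the three items are handled.

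The cost is SAP wording. Both sources are already collected, so no visit or form is added. The downsides are small. Result (b) uses a subset defined at baseline, captures attempts and not completed intercourse, and is unavailable at 6 weeks. It also includes women without a partner, whom the reason recorded with the added question can describe.
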